6.2. Sorafenib/placebo - dose modifications and delays

Sorafenib/placebo therapy will be taken according to defined dose levels:

Dose level 1 (starting dose) : 2 tablets / day (1-0-1)
 Dose level 2 (escalated dose): 3 tablets / day (1-0-2)
 Dose level 3 (targeted dose) : 4 tablets / day (2-0-2)

The starting dose will be dose level 1 in order to allow adaption to the drug and avoid acute toxicities. If after the run-in phase of 2 weeks dose level 1 was well tolerated (no probably related AE's > grade 1), the next dose level (dose level 2) will be commenced and maintained for the next 4 weeks. If, after this time, dose level 2 was well tolerated the targeted standard dose level (dose level 3) will be administered indefinitely. Dose level 3 is the targeted dose.

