6.2.1. Dose delay and modifications for non-hematological toxicity

In case of severe toxicities, dose reductions or delays will be required as specified in Table 2. It illustrates dose modifications for all non-hematologic toxicities according to CTCAE Version 4.02 in the CRF, except for skin toxicities, which will be detailed separately below. These recommendations pertain, if the adverse event is considered related to sorafenib.

Table 2: Non-hematologic criteria for dose delay and dose modification of sorafenib (except skin toxicity)^a

Grade	Dose Delay	Dose modification
0-2	none	No change
3	Interrupt until \leq grade 2 ^b	Resume with one dose level below last dose level ^c
4	OFF protocol therapy	OFF protocol therapy

a. Excludes nausea/vomiting that has not been pre-medicated, and diarrhea.

b. If no recovery within an up to 28-day delay, treatment will be permanently terminated unless the patient is deriving clinical benefit

c. The dose of study drug may be increased from the reduced dose level stepwise every 4 weeks to dose level 3 if tolerated (no re-appearance of non-hematological toxicity \geq grade 0-2). In case toxicity recurs, and repeated dose reductions are required (more than 2), treatment will be indefinitely performed with dose level 1. When this is also not tolerated study treatment will be permanently discontinued.

For the purpose of dose modifications, patients experiencing Hand-Foot syndrome should have their signs and symptoms graded according to the following system (see below). Other skin toxicities will be graded according to CTCAE Version 4.02.

- Grading for Hand-Foot Syndrome

Grade 1

Numbness, dysesthesia/paresthesia, tingling, painless swelling or erythema of the hands and/or feet and/or discomfort, which does not disrupt normal activities.

Grade 2

Painful erythema and swelling of the hands and/or feet and/or discomfort affecting the patient's activities.

Grade 3

Moist desquamation, ulceration, blistering or severe pain of the hands and/or feet and/or severe discomfort, which cause the patient to be unable to work or perform activities of daily living.

According to the grade and incidence of skin toxicity (including rash and hand-foot syndrome) for a given patient, the following dose modification schedule will be followed (see Table 3).

Table 3: Skin Toxicity Criteria for Dose Modification of Sorafenib

Toxicity Grade	Dose modification	Dose level after interruption

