Grade 1	Maintain dose level	Institute supportive measures
Grade 2 1 st appearance	Interrupt until resolved to grade 0-1	Resume with one dose level below the dose level prior to interruption ^a
2 nd or 3 rd appearance	Interrupt until resolved to grade 0-1	Resume with dose level 1 and maintain indefinitely
4th appearance	Decision whether to discontinue treatment permanently	
Grade 3 1 st appearance	Interrupt until resolved to grade 0-1	Resume with one dose level below the dose level prior to interruption ^a
2 nd appearance	Interrupt until resolved to grade 0-1	Resume with dose level 1 and maintain indefinitely
3 rd appearance	Decision whether to discontinue treatment permanently	

^a For patients who require a dose reduction for grade 2 or 3 rash or hand-foot syndrome, the dose of study drug may be increased subsequently to the targeted dose level after 4 weeks of therapy at the reduced dose without the appearance of rash or hand foot syndrome \geq grade 1.

Patients with discomfort due to hand foot syndrome may be treated with topical emollients, low potency topical steroids, or urea-containing cream; emollients and urea cream can be used early as a prophylactic measures to prevent extensive skin toxicity (see also

prophylactic measures [26] [27] [28]. All other grade 3 toxicities related to study drug result in a permanent dose reduction.

- Sorafenib-associated diarrhea

Diarrhea is a common side effect of sorafenib but is usually of low-to-moderate grade. It either resolves while treatment is continued, with appropriate anti-diarrhoic treatments, or once sorafenib is discontinued.

Appropriate prophylactic and/or therapeutic drugs that have been reported to be effective in the treatment of sorafenib-associated diarrhea are loperamide (4 mg after first loose stool, 2 mg after every other loose stool) or racecadotril (Tiorfan®) (one 100mg capsule three times daily). *However, an important differential diagnosis of Sorafenib associated diarrhoea in the context of allo-SCT is intestinal GvHD, which should be histologically confirmed or excluded via endoscopy of the sigmoid / colon.*

- Sorafenib-associated hypertension

The dose modification schedule for treatment emergent **hypertension** during sorafenib dosing should be followed (see table 4). Patients' blood pressure (BP) measurements will be monitored and appropriate treatment to effectively control hypertension under sorafenib-treatment is strongly recommended.

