Blood pressure measurements considered out of normal range are diastolic ≥ 100 mmHg and systolic ≥ 160 mmHg, or a ≥ 20 mmHg increase in diastolic measurement if the measurement was previously within normal limits.

Table 4: Management of Treatment-Emergent Hypertension

Grade of Event (NCI-CTCAE V4.02)	Management/Next Dose
Grade 1 asymptomatic and transient	Consider increased BP monitoring
Grade 2 asymptomatic and diastolic BP <110 mmHg	Begin anti-hypertensive therapy and continue sorafenib/placebo
Grade 2 symptomatic/persistent OR Diastolic BP ≥ 110 mmHg OR Grade 3	Sorafenib/placebo should be stopped* until symptoms resolve and diastolic BP returns to ≤ 100 mmHg. Treat patient with anti-hypertensives and when sorafenib/placebo is restarted, reduce by 1 dose level.** (refer to section 7.3) If diastolic BP not controlled to ≤ 100 mmHg on therapy, reduce sorafenib/placebo by another dose level and monitor BP closely***
Grade 4 life-threatening	Discontinue protocol therapy

Please note that specific criteria are not completely identical to NCI-CTCAE V4.02 criteria.

* Patients requiring a delay of >28 days should discontinue the study treatment

** May be able to resume full dose later.

*** Patients requiring >2 dose reductions should discontinue the study treatment.

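### Section 6.2.1 leaves dose re-escalation unclear in three places: permanent versus reversible grade 3 reductions, no cut-off grade in Table 2 footnote c, and a permitted jump from level 1 to level 3 in Table 3

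*Protocol*

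**What the plan says.** Section 6.2 sets three dose levels of 2, 3 and 4 tablets of 200 mg per day (400, 600 and 800 mg). Level 3 is the target and is conditional on the level below: "If, after this time, dose level 2 was well tolerated the targeted standard dose level (dose level 3) will be administered".

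Section 6.2.1 then handles toxicity:

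- **Table 2** applies to sorafenib-related non-hematologic events other than skin. Its footnote a also excludes diarrhea and nausea or vomiting without premedication. Grade 3 leads to a one-level reduction, after which, under footnote c, the dose "may be increased from the reduced dose level stepwise every 4 weeks to dose level 3 if tolerated". The condition is "no re-appearance of non-hematological toxicity" at a threshold printed as ≥ grade 0-2.
- **Table 3** covers all skin toxicity: "According to the grade and incidence of skin toxicity (including rash and hand-foot syndrome) for a given patient". Its footnote a opens with "For patients who require a dose reduction for grade 2 or 3 rash or hand-foot syndrome" and says the dose "may be increased subsequently to the targeted dose level after 4 weeks of therapy at the reduced dose", provided no rash or hand-foot syndrome of grade 1 or higher appears.
- **The sentence closing the skin text** reads: "All other grade 3 toxicities related to study drug result in a permanent dose reduction".
- **Table 4** reduces the dose by one level for a row that includes grade 3 hypertension. Its double-asterisk note adds: "May be able to resume full dose later".

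**The concern.** The first two rules leave a site without a definite instruction, and the third permits a step that looks unintended.

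After a drug-related grade 3 event covered by Table 2, or grade 3 hypertension, a site that takes the closing sentence literally keeps the reduced dose. A site that follows the table notes may return the patient to the dose at which the event occurred. Each can cite section 6.2.1, and no order of precedence is stated. Footnote c does not say which recurrence rules out an increase. Footnote a allows the daily dose to be doubled in one step in a patient who has just had grade 2 or 3 skin toxicity at the intermediate level.

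At stake are re-exposure to a dose that was not tolerated, avoidable loss of active drug, and consistency across the 10 to 20 planned centres. The per-protocol set (section 11.1) excludes major protocol violations, and dosing deviations are harder to judge against an unclear rule.

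**Working it through.** **1. Permanent or reversible**

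| Drug-related grade 3 event | Closing sentence, read literally | Specific rule | Conflict? |
|---|---|---|---|
| Covered by Table 2 | permanent | footnote c: may return to level 3 | yes |
| Hypertension | permanent | Table 4 note: full dose possible later | yes |
| Rash, hand-foot syndrome | not among the others | Table 3 footnote a | no |
| Other skin toxicity | permanent | Table 3, no re-escalation for these | no |
| Diarrhea; nausea/vomiting without premedication | permanent | no other dose rule | no |
| Hematologic | permanent | Table 5: one level down, no re-escalation rule | no |

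That the notes are only permissions does not reconcile them with the sentence, because a reduction that may be reversed is not permanent. Footnote c also has a rule for more than two reductions. From level 3, two reductions already reach level 1, so that rule has work to do only if the dose has risen in between. Table 2 was evidently drafted with re-escalation in mind. The Table 4 cell refers to a section 7.3, but section 7 ends at 7.2.2, so that pointer settles nothing.

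*Illustrative size.* Let d be the days left to month 24, with a month of 30.4375 days. Assume no interruption, no recurrence and the earliest permitted increase.

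From level 3: permanent = 600d mg; reversible = 600 × 28 + 800 × (d − 28) mg.

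| Event | d | Permanent | Reversible | Less drug |
|---|---|---|---|---|
| Month 1.5 | 684.8 | 410.9 g | 542.3 g | 24.2% |
| Month 12 | 365.2 | 219.2 g | 286.6 g | 23.5% |
| Month 18 | 182.6 | 109.6 g | 140.5 g | 22.0% |
| 91 days left | 91 | 54.6 g | 67.2 g | 18.8% |
| 28 days or fewer left | ≤ 28 | same | same | 0% |

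From level 2: permanent = 400d mg; stepwise = 400 × 28 + 600 × 28 + 800 × (d − 56) mg. At d = 688.5 (end of week 6) this is 275.4 against 534.0 g, 48.4% less. At d = 182.6 it is 73.0 against 129.3 g, 43.5% less.

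**2. The cut-off in footnote c**

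Read as ≥ grade 0, the condition can never be satisfied and no increase is ever allowed. Cut-offs of ≥ 1, ≥ 2 and above 2 remain arguable. Above grade 2 fits best: Table 2 treats grades 0-2 as one band with no dose change, and footnote c goes on to speak of repeated reductions, which Table 2 requires only at grade 3. This is not conclusive. In Table 3, grade 1 leaves the dose unchanged, yet footnote a still bars an increase at grade 1 or higher.

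**3. The jump in footnote a**

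Counting appearances separately for each grade, as Table 3's rows do, two kinds of path end at level 1 with footnote a attached:

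- a first grade 2 or first grade 3 event at level 2 (2 → 1);
- a first event of one grade at level 3 (3 → 2), then a first event of the other grade at level 2 (2 → 1).

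A second event of the same grade leads to level 1 indefinitely and is not affected.

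On these paths footnote a permits 400 → 800 mg/day: +100% in one step, and 800/600 = 33% above the level of the last event. Stepwise it would be +50%, then +33%. The difference in drug is 28 days × 200 mg = 5.6 g for d ≥ 56. As a share of the drug remaining with the jump, 400 × 28 + 800 × (d − 28) mg:

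- d = 688.5: 5.6/539.6 = 1.0%
- d = 182.6: 5.6/134.9 = 4.2%
- d = 91: 5.6/61.6 = 9.1%

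**The case against.** The strongest reply is that the closing sentence belongs to the skin text. Section 6.2.1 announces that skin toxicity is handled separately, and the sentence ends that part, just before the diarrhea item. Table 3 covers all skin toxicity while footnote a re-escalates only rash and hand-foot syndrome, so the other toxicities are naturally the remaining skin ones. On that reading the conflict with Tables 2 and 4 disappears. This is plausible, and it is why the point is an ambiguity and not a proven contradiction. But the sentence does not state the limit, and a site has no stated ground for supplying it.

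A reader might also infer that every grade 3 non-skin event is caught in the conflict. The documents do not support that. Diarrhea and nausea or vomiting without premedication lie outside Table 2, and Table 5 has no re-escalation rule for permanence to contradict.

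On the cut-off, it is fair to call ≥ grade 0-2 a drafting slip for above grade 2. That is the best guess, but the text as printed does not say it.

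On the jump, one can argue that footnote a names only an end point and that section 6.2 makes level 3 conditional on tolerating level 2. However, that condition is written for the initial escalation, whereas footnote a is the specific rule after skin toxicity. It omits the stepwise requirement that Table 2 footnote c contains. The jump is permitted, not required.

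**Conclusion.** The point stands as three wording defects in the dosing rules. The conflict over permanence holds on the literal reading only, and only for events covered by Table 2 and for grade 3 hypertension. The missing cut-off holds on any reading of the text as printed. The one-step doubling is permitted on the two kinds of path shown, the second of which rests on counting appearances by grade.

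On the literal reading, permanence costs at most about 24% of the remaining drug from level 3 and about 48% from level 2. These are illustrative upper bounds: they assume treatment to month 24, no interruption (although the tables require one for most of these events), no recurrence and the earliest optional increase. They apply to the sorafenib arm only. The protocol gives no expected number of patients on these paths. A reader might infer from the percentages that the trial's power is at risk, but nothing in the documents supports that: the sample size and type I error do not depend on these rules. The wording should be corrected because it affects patient safety and consistency between sites.

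**What to change.** 1. **Closing sentence.** Keep it and add: *unless Table 2 footnote c, Table 3 footnote a or the double-asterisk note to Table 4 allows re-escalation.* Deleting it or narrowing it to skin would remove the only dose-reduction text that reaches grade 3 diarrhea. The cost is that some patients may be re-exposed to the dose at which the event occurred, as the table notes already allow. If the sponsor wants permanence for all grade 3 events, the permissions in Tables 2 and 4 must go instead, at the loss of drug shown above.
2. **Table 2 footnote c.** Replace ≥ grade 0-2 with one grade. Above grade 2 (≥ grade 3) fits the table's band for grades 0-2; the sponsor may choose the stricter ≥ grade 2. The higher cut-off allows increases despite recurring grade 2 toxicity, and the lower one keeps more patients on a reduced dose.
3. **Table 3 footnote a.** Reword to: *may be increased by one dose level after each 4 weeks without rash or hand-foot syndrome ≥ grade 1, up to the targeted dose level.* Affected patients reach level 3 about 4 weeks later, with 5.6 g less drug each, about 1% of the remainder for an event in weeks 3-6.

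In all, one sentence and two footnotes change.

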5.3. Exclusion criteria

- Any severe concomitant conditions which make it undesirable for the patient to participate in the study or which could jeopardize compliance with the protocol (such as substance abuse, uncontrolled infection, known HIV, HBV, HCV infection).
- Psychiatric disorder that interferes with ability to understand the study and give informed consent, and/or impacts study participation or follow-up.
- Cardiac disease: heart failure NYHA III/IV, unstable coronary artery disease (MI more than 6 months prior to study entry is permitted), serious cardiac ventricular arrhythmias requiring anti-arrhythmic therapy (beta-blockers or digoxin are permitted).
- Resting blood pressure consistently higher than systolic 150 mmHg and/or diastolic 90 mmHg despite antihypertensive therapy
- Patients undergoing renal dialysis
- Evidence or history of severe non-leukemia associated bleeding diathesis or coagulopathy
- Patients with uncontrolled seizure disorder despite medication
- History of organ allograft (except for allogenic SCTX)

- Patients with major surgery, open biopsy, or significant traumatic injury within 4 weeks prior to start of first dose of study drug
- Serious non-healing wound, ulcer or bone fracture
- Known Flt3-kinase inhibitor resistance
- Previous Sorafenib therapy
- Active (uncontrolled) graft versus host disease GvHD (> grade I) at time of randomization despite the use of adequate therapeutic measures
- Investigational drug therapy outside of this trial during or within 4 weeks of study entry
- Pregnancy or breast feeding
- Allergy to study medication or compositions of excipients in study medication
- Secondary allo-SCT
- Previous or concurrent cancer curatively treated ≤ 3 years prior to study entry

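### Section 6.2.1 gives conflicting stop and continue instructions for sorafenib-related hypertension, within Table 4 and between Tables 2 and 4, and cites a section that does not exist

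*Protocol*

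**What the plan says.** Section 6.2.1 of the protocol holds three non-hematologic dose-modification tables. The lead-in to Table 2 sets its scope: "It illustrates dose modifications for all non-hematologic toxicities according to CTCAE Version 4.02 in the CRF, except for skin toxicities". Footnote a narrows that scope once more: "Excludes nausea/vomiting that has not been pre-medicated, and diarrhea". Hypertension appears in neither exception. The lead-in adds that these recommendations apply when the event is judged related to sorafenib.

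Later in the section, a paragraph on sorafenib-associated hypertension directs the reader to Table 4. It defines out-of-range readings as "Blood pressure measurements considered out of normal range are diastolic ≥ 100 mmHg and systolic ≥ 160 mmHg", with a diastolic rise of 20 mmHg or more from a previously normal value as the alternative.

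Table 4 has four rows. The second is entered by "Grade 2 asymptomatic and diastolic BP <110 mmHg"; its action is to start antihypertensive treatment and carry on with study drug. The third is entered by "Grade 2 symptomatic/persistent OR Diastolic BP ≥ 110 mmHg OR Grade 3"; its action is to stop study drug until symptoms have resolved and diastolic pressure is back to 100 mmHg or less, then restart one dose level lower. That third row refers the reader to section 7.3.

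**The concern.** An investigator needs one answer for one event. Here the same grade 2 reading can satisfy a row that continues study drug and a row that stops it, and a second table that also covers the event can give a different answer again. The choice lies between continuing, interrupting with a dose reduction, and permanent discontinuation, so both patient safety and exposure depend on it. Conduct also becomes hard to judge: an action that follows one row or table departs from another, so the protocol does not say whether it is a deviation.

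**Working it through.** No figure in the plan has to be reproduced here. The check is a literal reading of the two tables.

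**Step 1: overlap inside Table 4.** Rows 2 and 3 were applied to every combination of grade (1 to 4), symptoms (yes/no), persistence (yes/no) and diastolic pressure at or above 110 mmHg (yes/no): 4 × 2 × 2 × 2 = 32 combinations, some of which may not occur in practice. Row 2 sets conditions on symptoms and diastolic pressure but is silent on persistence. Row 3 accepts persistence as sufficient for grade 2. The two rows therefore meet in exactly one combination: grade 2, asymptomatic, persistent, diastolic below 110 mmHg. Nothing says which row wins.

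**Step 2: Table 2 against Table 4 for grade 2.** Table 2 gives no delay and no dose change for every grade 2 event. The eight grade 2 combinations in Table 4 split as follows:

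- 1 meets row 2 only (asymptomatic, not persistent, below 110 mmHg): continue, which agrees with Table 2.
- 1 meets rows 2 and 3: the overlap from Step 1.
- 6 meet row 3 only: stop and reduce, against no change in Table 2.

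These are counts of combinations, not of patients.

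**Step 3: the remaining rules side by side.**

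| Situation | Table 2 | Table 4 |
|---|---|---|
| Grade 2 symptomatic, persistent or diastolic ≥ 110 mmHg | No delay, no change | Stop, restart one level lower (row 3) |
| Grade 3, when to restart | At grade 2 or below | Symptoms resolved and diastolic ≤ 100 mmHg |
| More than 2 reductions | "treatment will be indefinitely performed with dose level 1"; discontinue only if that is not tolerated | Discontinue |
| No recovery by 28 days | "treatment will be permanently terminated unless the patient is deriving clinical benefit" | Discontinue, no exception stated |
| Grade 4 | Off protocol therapy | Discontinue |

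Only the grade 4 line agrees fully. For grade 3 both tables interrupt and resume one level lower, so the difference is confined to the restart criterion.

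**Step 4: size of one dose level.** Section 6.2 sets level 1 at 2 tablets a day, level 2 at 3 and level 3 at 4.

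- Level 3 to level 2: (4 − 3) / 4 = 25% of the daily dose.
- Level 2 to level 1: (3 − 2) / 3 = 33% of the daily dose.

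**Step 5: cross-reference.** Both the table of contents and the body end section 7 at 7.2.2 and go on to section 8. There is no section 7.3.

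**The case against.** The best defence is that the hypertension paragraph names Table 4 as the schedule to follow, and a specific instruction normally governs over a general one. Most readers would probably apply Table 4. That weakens the conflict between the tables but does not remove it: the section carves out skin toxicity, nausea/vomiting and diarrhea from Table 2 explicitly, leaves hypertension in, and nowhere says that Table 4 replaces Table 2. Nor does the argument touch the overlap inside Table 4.

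Some stronger readings are tempting, and the document does not support them:

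- **That the tables oppose each other throughout.** They do not. Uncomplicated grade 2 and grade 4 agree, and grade 3 differs only in the restart criterion and in the rules for repeated reductions and long delays.
- **That the out-of-range definition always needs systolic and diastolic criteria together, so a systolic rise goes unmanaged.** The sentence has a second limb that a diastolic rise alone satisfies. No Table 4 row uses the definition; rows are entered by grade, symptoms, persistence and diastolic value. A systolic rise can enter through its grade, and the grading criteria are not in the document.
- **That the definition contradicts section 5.3** ("Resting blood pressure consistently higher than systolic 150 mmHg and/or diastolic 90 mmHg despite antihypertensive therapy"). That is an eligibility rule for sustained pressure despite treatment; the definition describes readings during treatment. Different limits and connectives are not in themselves a contradiction.
- **That sites do manage patients differently.** This is a plausible consequence of two rows applying at once, but the document does not show it.

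**Conclusion.** The point holds as a contradiction in written stop and continue rules. Rows 2 and 3 of Table 4 collide in one combination, whichever table prevails. Tables 2 and 4 differ in four situations: complicated grade 2, the grade 3 restart criterion, more than two reductions, and 28 days without recovery. The cross-reference to section 7.3 leads nowhere.

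For a patient in one of these situations, the difference ranges from no change to an interruption followed by a 25% or 33% lower daily dose, or from staying on level 1 to permanent discontinuation. The protocol gives no expected rate of hypertension, so the number of patients concerned is unknown, and no effect on the comparison of relapse-free survival is shown.

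The conclusion rests on a literal reading of both tables and, for the conflict between them, on the event being judged related to sorafenib. It takes no view on which clinical rule is right.

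**What to change.** Reconcile the passages of section 6.2.1 by amendment:

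1. State which table governs sorafenib-related hypertension, covering grade 2, the grade 3 restart criterion, repeated reductions and delays beyond 28 days, and make the Table 2 lead-in and footnote a consistent with that statement.
2. Reword the two grade 2 rows of Table 4 so that no patient can meet both, with persistence addressed in each.
3. Correct or delete the reference to section 7.3.

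The thresholds and the choice between continuing, reducing and stopping are for the sponsor to set. The cost is a wording amendment. No visit, test or data item is added, because the visit schedule already includes blood pressure at every treatment visit.
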